2.3.4 Dose Selection

The initial doses of blinatumomab, nivolumab, and ipilimumab to be used in this trial have been selected based on the results of prior trials demonstrating the safety of these drugs at the selected doses as well as the efficacy of blinatumomab at the selected dose in the treatment of ALL. All participants in this study will receive blinatumomab using the standard dosing regimen that has been FDA approved for the treatment of relapsed and/or refractory ALL based on the results of two Phase II trials.^{31,32} As blinatumomab is the only agent in this trial that is known to have significant activity in ALL, it is critical that its dose remain unchanged. Nivolumab will initially be given in combination with blinatumomab at a flat dose of 240 mg every two weeks.

Population pharmacokinetics support the flat dose of 240 mg as being identical to 3 mg/kg for subjects weighing 80 kg, which was identified as a safe dose of nivolumab in the initial phase I trial.^{35,51} Furthermore, data from the phase I trial of nivolumab suggest that its side effects are not dose-dependent, so lower doses may not mitigate toxicities even when combined with blinatumomab. However, if significant toxicities should arise at a flat dose of 240 mg every 2 weeks of nivolumab, then further patients will be treated at a de-escalated nivolumab dose of 80 mg every 2 weeks. In combination with nivolumab and blinatumomab, ipilimumab will first be given at a dose of 1 mg/kg every 6 weeks with escalation in subsequent patients to a dose of 3 mg/kg every 6 weeks, if the initial dose proves tolerable in combination with nivolumab and blinatumomab. This differs from a recent phase III study combining nivolumab and ipilimumab in metastatic melanoma that used an ipilimumab dose of 3 mg/kg every 3 weeks with 1 mg/kg every 3 weeks of nivolumab.⁵⁸ However, in the initial phase I study combining ipilimumab and nivolumab for the treatment of metastatic melanoma, nearly all treatment-related adverse events were reduced in patients who received 1 mg/kg of ipilimumab with 3 mg/kg of nivolumab every 3 weeks as compared to those who received 3 mg/kg of ipilimumab with 1 mg/kg of nivolumab every 3 weeks, although the objective response rate was comparable.³⁶ Furthermore, the reported half-life of ipilimumab is 15.4 days, and the combination with nivolumab does not seem to effect the clearance of ipilimumab.⁵² Thus the decreased dose density of ipilimumab proposed in this study has strong biologic rationale and should help to mitigate the toxicities of ipilimumab.

2.4 Correlative Studies Background

The goal of the correlative studies in this trial will be to characterize the effect of treatment on T cells particularly on their re-distribution, in vivo expansion, activation, and effector differentiation in both the BM and PB compartments over time. This has recently been studied extensively by our group in AML, but there is currently a paucity of data in ALL. Thus the correlative studies are designed to gain insight about T-cell function in ALL patients prior to treatment, during blinatumomab monotherapy, following the addition of immune checkpoint inhibitors to blinatumomab, at the conclusion of treatment, and at the time of relapse. These studies will also characterize the effects of these treatments on co-signaling molecule expression and the expression of transcription factors in T-cell subpopulations. These investigations will not be limited to the immune inhibitory pathways for which there are currently commercially available inhibitors (i.e. PD-1/PD-L1 and CTLA-4/CD80/CD86), as inhibitors of many other pathways are currently in development, and we expect that interrogation of other pathways will identify potential future targets for immune checkpoint inhibition.

2.4.1 **Dynamics of lymphocyte subpopulations in both peripheral blood and the bone marrow microenvironment pre- and post-blinatumomab and immune checkpoint inhibitor(s) treatment.**

Current data from patients treated with blinatumomab suggests tri-phasic T-cell kinetics: T-cell counts decline within hours after the start of blinatumomab infusion, recover to baseline within a few days followed by T-cell expansion with, on average, more than doubling of T-cell counts at 2-3 weeks under continued infusion of blinatumomab, and lastly T-cell contraction in between cycles. Patients who achieved MRD clearance following blinatumomab and were long-term survivors had a higher degree of T-cell and T_{EM}-cell expansion after the first two treatment

cycles compared to patients having MRD response but short survival or non-responders.³⁴ This implies that T-cell expansion might be a key factor for improving response and survival of relapsed/refractory ALL patients after blinatumomab immunotherapy. In terms of T-cell subpopulations, T-cell expansion was associated with increases in CD3⁺ T_{EM}, CD8⁺ T_{EM}, CD8⁺ T_{EMRA}, CD4⁺ T_{CM} cells.⁸² There are limited data on the relevance of other T-cell subpopulations except a suggestion from a small study of ALL patients refractory to blinatumomab therapy that a high percentage of Tregs can predict a lack of response to therapy.⁸³ In terms of checkpoint inhibitors, the absolute lymphocyte count (ALC) has been found to be a specific pharmacodynamic biomarker of ipilimumab, and the degree of increase in the ALC has been associated with survival in patients with melanoma.⁸⁴⁻⁸⁶ Ipilimumab administration is followed by enhanced T-cell proliferation and a rise in CD8⁺ T_{CM} and CD4⁺ T_{EM} cells.^{87,88} Ipilimumab-induced changes in Tregs have been more controversial across different studies with both decreases and increases in circulating FoxP3⁺Tregs observed in patients responding to treatment.^{84,89} In contrast to ipilimumab, data on the predictive role of immune cell subsets and changes in ALC in cancer patients during PD-1 or PD-L1 blockade are lacking. In addition, no association between ALC and clinical response was observed when nivolumab and ipilimumab were administered in combination, suggesting that the combination of these two antibodies generated immune responses with unique features compared to their administration as monotherapy.³⁶

We anticipate that the addition of nivolumab or nivolumab/ipilimumab to blinatumomab will be associated with increased T-cell effector differentiation and proliferation and improved post-treatment antitumor responses. Thus we propose monitoring of T-cell dynamics during treatment as an integrated biomarker to support the collection of mandatory PB and BM specimens.

The overarching goals of these studies are to: a) characterize the effect of blinatumomab in combination with checkpoint inhibition on T cells particularly on their re-distribution, *in vivo* expansion, activation, and effector differentiation in both PB and BM compartment over time and in relation to the response to therapy. We will also examine functional dynamics of Tregs and their fractions, B cells, and NK cells; b) identify potential predictive biomarker candidates (in combination with studies in Section 2.4.2) to guide improved selection of ALL patients who are more likely to benefit from addition of checkpoint inhibitors to blinatumomab therapy; c) characterize the mechanisms of relapse / refractoriness to blinatumomab combined with checkpoint inhibition such as T-cell dysfunction.

Our expectation is that the treatment strategy being investigated in this study will enable ALL patients who would not respond to a single-agent blinatumomab to respond to the combination of blinatumomab and immune checkpoint inhibition, and even enhance the depth and durability of response in those patients who may be responders to blinatumomab alone.

2.4.2 **Changes in T-cell co-signaling receptors and canonic transcription factor expression in defined T cell subpopulations in both peripheral blood and bone marrow pre- and post-blinatumomab and immune checkpoint inhibitor(s) therapy.**

Studies performed by us and others suggest the presence of multiple aberrations in T-cell co-

signaling receptors and canonic transcription factor expression in defined T-cell subpopulations in patients with AML but this has never been studied in depth in patients with ALL. Our group has shown that co-expression of a number of inhibitory receptors (iRs), such as CTLA-4, PD-1, TIM-3, 2B4 or BTLA, on T cells in patients with AML differs between PB and BM and changes through the course of the treatment.⁷⁴ Recent reports provided several lines of evidence that immune checkpoint pathways are also operational in ALL and may represent a potential mechanism of therapeutic resistance, including to blinatumomab. First, PD-1 but also other co-inhibitory molecule such as Tim-3 were more highly expressed (and co-expressed) on T cells from ALL patients compared to healthy controls.⁷⁶ Second, an increase in PD-1 expression on BM lymphocytes was noted at the time of therapeutic failure.⁷⁵ Finally, in functional studies, the blinatumomab effect on T cells (proliferation and interferon- γ production) *in vitro* appeared to be target cell-dependent and correlated with the target cell-expression of co-signaling molecules. Combined inhibition of the PD-1 and CTLA-4 pathways with blinatumomab enhanced effector T-cell function of healthy donors and patient's T cells against ALL target cells more than PD-1 inhibition alone while inhibition of co-stimulatory CD28-CD80/86 interactions downregulated T-cell effector function and proliferation.⁷⁶

Thus we anticipate that administration of blinatumomab in combination with checkpoint inhibitors should result in strong T-cell differentiation and expansion and potent anti-leukemia activity. Whether the expression of iRs differs in patients with ALL at presentation and relapse and what is the effect of therapy is unknown. As a part of this proposal we will conduct comprehensive analysis of signaling receptors and canonic transcription factor expression in defined T-cell subpopulations in both PB and BM before and post-blinatumomab and immune checkpoint inhibitor therapy. This represents a very relevant unmet need for future integration of checkpoint inhibitors or any other immunotherapy approaches seeking to overcome T-cell exhaustion, increase the response rates to therapies, and/or maintain remission in ALL. Thus, in addition to studies proposed in Section 2.4.1, we propose monitoring the dynamics of signaling receptors and canonic transcription factors expression in defined T-cell subpopulations during treatment as an integrated biomarker to support the collection of mandatory PB and BM specimens. As discussed in Section 2.4.1, the main goals of these studies are to characterize the effect of blinatumomab in combination with checkpoint inhibition on T-cell dynamics (re-distribution, *in vivo* expansion, activation, and effector differentiation) but also on expression of co-signaling molecules in both PB and BM compartment over time, to identify potential predictive biomarker candidates to guide better selection of ALL patients who are more likely to benefit from the addition of checkpoint inhibitors to blinatumomab therapy, and to characterize the mechanisms of relapse / refractoriness after blinatumomab combined with checkpoint inhibition such as T-cell dysfunction.

2.4.3 Expression of co-signaling molecules on leukemia blasts (CD10⁺/CD19⁺/CD34⁺) before and after treatment with blinatumomab and checkpoint inhibitors.

Upregulation of programmed death-ligand 1 (PD-L1) on tumor cells in response to endogenous anti-tumor immunity inhibits adaptive immune responses by inducing T-cell dysfunction. Expression of PD-L1 on tumor cells has been associated with poor outcome in solid cancers as well as hematologic malignancies. Overall, cytokine-induced PD-L1 expression on tumors represents evasion of tumor immunity termed “adaptive resistance.” Several lines of evidence

2.4.4 Cytokine studies

Blinatumomab treatment has been associated with transient release of cytokines such as IL-2, IL-6, IL-10, IFN- γ and TNF- α . However, there was not a clear pattern of cytokine release and response.⁸² Administration of novel immunotherapeutics, including immune checkpoint inhibitors, alone or in combination with chemotherapy have resulted in systemic immune-related AEs.⁹⁰ Whether administration of nivolumab and nivolumab/ipilimumab following blinatumomab will increase cytokine expression and if increases in cytokines will be associated with toxicity is unknown. Thus, we will be collecting and storing serial plasma samples (at the time of PB collection) and if there is a strong rationale we will conduct measurement of cytokines to assess blinatumomab and checkpoint inhibitors-induced global T-cell activation. We will examine the levels of cytokines before and after treatment with blinatumomab and checkpoint inhibitors, including the levels of sCTLA-4. In particular, sCTLA-4 is found at a significantly higher frequency in ALL patients than healthy controls, and higher levels of sCTLA-4 correlate with relapse risk and the probability of survival following treatment.^{77,78} Experimental evidence suggests that current anti-CTLA-4 antibodies bind both sCTLA-4 and membrane-bound CTLA-4 and as such that their administration may improve the immune recognition of ALL cells.⁷⁹ We anticipate that the levels of sCTLA-4 may decrease upon ipilimumab treatment.

2.4.5 **Immune profiling of T cell repertoire and characterize T cell transcriptional signature before and after treatment**

2.4.5.1 Immune Profiling of T-cell repertoire

High throughput deep sequencing of the TCRV- β CDR3 region is very valuable technology to better characterize the T-cell repertoire changes after checkpoint inhibitor administration. The best metric of TCR repertoire diversity are changes in clonality index and repertoire diversification. This strategy is being increasingly used to assess T-cell repertoire changes in both periphery and intra-tumor environment providing critical mechanistic clues. Previous studies have shown that ipilimumab leads to TCR diversification and the induction of new tumor-antigen specific T-cell responses as early as two weeks after first administration.⁹¹⁻⁹³ However, it remains unclear how simultaneous use of multiple immunotherapeutics will affect the TCR repertoire and if standardized metrics will correlate with toxicity or clinical response. We anticipate that treatment with blinatumomab will lead to diversification of the TCR repertoire that would be further modeled by checkpoint inhibitors. The studies proposed in this protocol will evaluate TCR diversity in T cells isolated from PB and BM from patients before and after treatment with blinatumomab and checkpoint inhibitors on the parent clinical trial. We will determine TCR diversity and clonal composition using a molecular and computational approach based on high-throughput DNA sequencing of rearranged TCR β CDR3 regions from T-cell genomic DNA. The findings derived from these analyses are meant to generate hypotheses and will be expanded upon with additional studies.

2.4.5.2 Characterization of T-cell transcriptional signature before and after treatment

We have substantial experience with this approach from our ongoing analysis of T-cell dysfunction in patients with AML (data not shown). We now have evidence at the transcriptional level that CD8⁺ T cells from AML patients have significant up-regulation of genes involved in T-cell co-inhibition and transcription factors associated with T-cell exhaustion when compared to healthy controls. Serial gene expression analysis of CD8⁺ T cells (at diagnosis and after induction chemotherapy) using the Human Prime View Gene Expression Array (<http://www.affymetrix.com>) revealed that CD8⁺ T-cell gene signatures differ in patients who achieve complete response versus non responding (NR) patients at the time of response assessment. Most strikingly, the set of genes up-regulated in responding patients clustered together with healthy controls, whereas NR patients clustered separately.⁷⁴ Gene expression will be analyzed with focus on “pretreatment” and “response to treatment” analyses. We predict based on our previous work that several key co-stimulatory signaling pathways will be downregulated in CD8⁺ T cells retrieved from patients with ALL in comparison to healthy controls and that these pathways will differ after blinatumomab, nivolumab \pm ipilimumab administration. We will also examine whether there is differential-expression of genes between CD8⁺ T cells in BM relative to those in circulation. These studies are likely to provide important insights into the T-cell transcriptome in patients with ALL in particular as it relates to the immunomodulatory strategies to modulate their function. The goal of this analysis is to provide the biological understanding necessary for future clinical studies of blinatumomab and checkpoint inhibitors in ALL including improved selection of patients who may benefit from this therapeutic strategy.

2.5 Summary

Outcomes in relapsed or refractory ALL as well as outcomes for older patients who receive traditional induction chemotherapy remain poor with a significant risk of relapse and death.^{3-6,8,10} The novel BiTE antibody blinatumomab has recently demonstrated efficacy in both Ph-positive and Ph-negative Pre-B ALL that has relapsed or is refractory to treatment, but only half of the patients respond and the duration of remission from this treatment is typically short.^{33,94} Pre-clinical studies suggest that inhibition of PD-1/PD-L1 immune regulatory axis could augment the blinatumomab-initiated T-cell response, thereby overcoming a potential mechanism of blinatumomab resistance.^{75,76} There is also evidence that the CTLA-4/CD80/CD86 immune regulatory pathway is upregulated in ALL, suggesting that inhibition of this pathway in combination with blinatumomab could yield a more robust immune-mediated attack on CD19⁺ ALL cells.^{77,78} Combinations of the anti-PD1 antibody nivolumab and anti-CTLA4 antibody ipilimumab have demonstrated remarkable efficacy in melanoma with sustained responses and an acceptable side effect profile.⁵⁸ Thus there is strong rationale for combining blinatumomab with both single and dual immune checkpoint blockade in relapsed or refractory Pre-B ALL in the interest of increasing the frequency and duration of remissions by improving the T cell-mediated immune response to the underlying malignancy.

3. PATIENT SELECTION

3.1 Pre-Registration Eligibility Criteria

- 3.1.1 Patients must have suspected refractory or relapsed pre-B cell ALL or mixed phenotype acute leukemia (MPAL), or if newly diagnosed, the patient must be 60 years of age or older.
- 3.1.2 Bone marrow and/or peripheral blood specimens will be submitted for correlative studies as outlined in Section 9. Patients who have a dry tap will still be eligible.

3.2 Registration Eligibility Criteria

- 3.2.1 Patients must have histologically or cytologically confirmed by the local institution CD19⁺ Precursor B-acute lymphoblastic leukemia (Pre-B cell ALL) OR CD19⁺ mixed phenotype acute leukemia (MPAL): a) with relapse following or refractory to at least one prior line of therapy if older than 21 years; b) in second or higher relapse or refractory to at least two prior lines of therapy if 21 years old and younger (16-21); c) or they must have a new diagnosis of Pre-B cell ALL or CD19⁺ MPAL but are ≥ 60 years old and are either not a candidate for or do not wish to receive traditional induction chemotherapy.
- 3.2.2 The evidence of CD19⁺ expression on leukemia cells must be confirmed by pathology review of the bone marrow and/or peripheral blood specimens (flow cytometry and/or immunohistochemistry) collected at the time of current relapse and prior to the initiation of therapy.
- 3.2.3 Patients with Ph⁺ Pre-B cell ALL OR Ph⁺ MPAL will be eligible if they have been refractory to or intolerant of treatment with at least 1 second-generation or third-generation tyrosine kinase inhibitor (TKI).
- 3.2.4 Patients who were treated with blinatumomab in the past will be allowed on the study as long as they have persistent CD19 expression on leukemia cells and did not experience unacceptable toxicities with prior blinatumomab administration. Patients who were treated with chimeric antigen receptor (CAR)-modified T cells targeting CD19 in the past will be allowed on the study as long as they have persistent CD19 expression on leukemia cells.
- 3.2.5 Patients with a history of allogeneic HSCT will be eligible if they are more than 90 days removed from the date of stem cell infusion, have no evidence of acute graft-versus-host disease (GVHD) or active chronic (grade 2-4) GVHD, and are off of all transplant-related immunosuppression for at least 2 weeks.
- 3.2.6 Age ≥ 16 years. Because no dosing or adverse event data are currently available on the use of blinatumomab in combination with nivolumab \pm ipilimumab in pediatric patients, children are excluded from this study, but will be eligible for future pediatric trials.
- 3.2.7 ECOG/Karnofsky performance status of 0-2 (Karnofsky $\geq 60\%$, see Appendix A).

3.2.8 Life expectancy of greater than 12 weeks.

3.2.9 Patients must have normal organ function as defined below:

- total bilirubin ≤ 2.0 mg/dL (except patients with Gilbert Syndrome, who can have total bilirubin < 3.0 mg/dL)
 - AST(SGOT)/ALT(SGPT) $\leq 5 \times$ ULN
 - Serum creatinine $\leq 1.5 \times$ ULN
- OR
- creatinine clearance (CrCl) ≥ 50 mL/min (if using the Cockcroft-Gault formula below):

Female CrCl = $\frac{(140 - \text{age in years}) \times \text{weight in kg} \times 0.85}{72 \times \text{serum creatinine in mg/dL}}$

Male CrCl = $\frac{(140 - \text{age in years}) \times \text{weight in kg} \times 1.00}{72 \times \text{serum creatinine in mg/dL}}$

3.2.10 The effects of nivolumab, ipilimumab, and blinatumomab on the developing human fetus are unknown. For this reason, women of child-bearing potential (WOCBP) and men must agree to use adequate contraception (hormonal or barrier method of birth control; abstinence) prior to study entry and for the duration of study participation. WOCBP should use an adequate method to avoid pregnancy for 23 weeks after the last dose of investigational drug. Women of childbearing potential must have a negative serum or urine pregnancy test (minimum sensitivity 25 IU/L or equivalent units of HCG) within 24 hours prior to the start of treatment on the study. Women must not be breastfeeding. Men who are sexually active with WOCBP must use any contraceptive method with a failure rate of less than 1% per year. Men receiving nivolumab \pm ipilimumab and blinatumomab and who are sexually active with WOCBP will be instructed to adhere to contraception for a period of 31 weeks after the last dose of investigational product. Women who are not of childbearing potential (*i.e.*, who are postmenopausal or surgically sterile as well as azoospermic men) do not require contraception.

Note: Women of childbearing potential (WOCBP) is defined as any female who has experienced menarche and who has not undergone surgical sterilization (hysterectomy or bilateral oophorectomy) or who is not postmenopausal. Menopause is defined clinically as 12 months of amenorrhea in a woman over 45 in the absence of other biological or physiological causes. In addition, women under the age of 55 must have a documented serum follicle stimulating hormone (FSH) level less than 40 mIU/mL.

Should a woman become pregnant or suspect she is pregnant while she or her partner is participating in this study, she (or the participating partner) should inform the treating physician immediately.

3.2.11 Adequate pulmonary function as assessed by oxygen saturation $\geq 90\%$ when ambulating and not requiring supplemental oxygen.

- 3.2.12 Patients with a known history of testing positive for human immunodeficiency virus (HIV) or known acquired immunodeficiency syndrome (AIDS) will be eligible if:
1. They are generally healthy from an HIV perspective and on a stable antiretroviral regimen for >6 months.
 2. They have had no AIDS-defining conditions in the past 12 months other than historically low CD4+ cell counts.
 3. They have an undetectable viral load on standard assays.
- 3.2.13 Patients with a known history of hepatitis C (HCV) will be eligible if they have an undetectable viral load. If the patient received treatment for HCV, then that treatment must have been completed at least three weeks prior to enrollment.

3.2.14 Ability to understand and the willingness to sign a written informed consent document.

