- 3.3.8 Uncontrolled intercurrent illness including, but not limited to, active, uncontrolled infection; symptomatic congestive heart failure; unstable angina pectoris; cardiac arrhythmia; or psychiatric illness/social situations that would limit compliance with study requirements. Patients with infection under treatment and controlled with antibiotics are eligible.
- 3.3.9 Pregnant women are excluded from this study because nivolumab and ipilimumab have the potential for teratogenic or abortifacient effects. Because there is an unknown but potential risk for adverse events in nursing infants secondary to treatment of the mother with nivolumab and ipilimumab, breastfeeding should be discontinued if the mother is treated with nivolumab and ipilimumab. These potential risks may also apply to blinatumomab.
- 3.3.10 History of any chronic hepatitis including alcoholic, non-alcoholic steatohepatitis (NASH), drug related, autoimmune, chronic viral positive tests for hepatitis B virus surface antigen (HBsAg), hepatitis B core antibody (anti-HBc) in the absence of hepatitis B surface antibody (anti-HBs), or a positive hepatitis C (HCV) viral load. These patients are excluded due to the risk for autoimmune hepatitis with immune checkpoint inhibitors exacerbating their known liver disease as well as the unknown risk for hepatitis B and/or C reactivation with blinatumomab and immune checkpoint inhibitors.
- 3.3.11 Subjects with active autoimmune disease, a history of known or suspected autoimmune disease or a history of a syndrome requiring systemic corticosteroids (>10 mg daily of prednisone equivalent) except for the treatment of malignancy with the exception of:
- Isolated vitiligo
 - Resolved childhood atopy
 - History of a positive ANA titer without associated symptoms or history of symptoms of an autoimmune disorder
 - Controlled thyroid disorders
 - Type I diabetes mellitus
 - Psoriasis, Sjögren's syndrome, and arthropathies not requiring systemic treatment

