⁴ PT/PTT, fibrinogen and d-dimer will be measured prior to each cycle of blinatumomab. In cycle 1, due to higher risk for DIC because of active disease, PT/PTT, fibrinogen and d-dimer should be checked at least twice a week in the first two weeks. The frequency of measurement may be higher and adjusted for individual patient's need as per the SOC requirements for monitoring and treatment of patients with ALL.

⁵ Serum chemistry: albumin, alkaline phosphatase, total bilirubin, bicarbonate, BUN, calcium, chloride, creatinine, glucose, LDH, phosphorus, potassium, total protein, SGOT [AST], SGPT [ALT], sodium, uric acid. Serum chemistry will be performed on day 1 of each cycle, daily for the first 4 days of cycle 1, weekly during cycle 1 and 2, and every 2 weeks thereafter for the duration of therapy. Serum chemistry should be performed within three days of nivolumab and ipilimumab administration. The frequency of serum chemistry measurements may be higher and adjusted for individual patient's need as per the SOC requirements for monitoring and treatment of patients with ALL.

⁶ Amylase, lipase, and TSH should be checked within three days prior to each nivolumab administration. If TSH is abnormal, Free T3 (triiodothyronine) and T4 (thyroxine) should be assessed. Screening time point must be done within 28 days of registration.

⁷ Hepatitis serologies will be performed as baseline and include: Hepatitis B surface antigen (HBV sAg), Hepatitis B core antibody (anti-HBc), and Hepatitis surface antibody (HBsAb). Hepatitis C antibody (HCV Ab) and/or Hepatitis C RNA (HCV RNA). Screening time point must be done within 28 days of registration.

⁸ Quantitative immunoglobulin should be measured at baseline, at the end of cycle 1, at the end of the last blinatumomab cycle and every 3-6 months thereafter until off study. Screening time point must be done within 28 days of registration.

⁹ For WOCBP (women of childbearing potential) only: A serum or urine pregnancy testing is required prior to study enrollment and prior to each cycle.

¹⁰ Writing test (Appendix G) should be performed at baseline, prior to each cycle, and then weekly during blinatumomab administration (week1-4) in cycle 1 and 2 and every 2 weeks during blinatumomab administration (week 1-4) in cycle ≥ 3 of blinatumomab.

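### The FSH limit in the 3.2.10 menopause definition is an upper bound, so for some women aged 46 to 54 it sorts opposite to its confirmatory purpose

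*Combined protocol and SAP*

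**What the plan says.** The WOCBP note in section 3.2.10 gives the clinical rule first: "Menopause is defined clinically as 12 months of amenorrhea in a woman over 45 in the absence of other biological or physiological causes". The next sentence is introduced as an addition to that rule and says that "women under the age of 55 must have a documented serum follicle stimulating hormone (FSH) level less than 40 mIU/mL".

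The same note defines a WOCBP as a woman past menarche "who has not undergone surgical sterilization (hysterectomy or bilateral oophorectomy) or who is not postmenopausal". Three safeguards depend on the label:

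- **Contraception (3.2.10).** It is required of WOCBP during the study and for 23 weeks after the last dose. Women not of childbearing potential, among whom the section counts the postmenopausal and the surgically sterile, "do not require contraception".
- **Test at entry (3.2.10).** "Women of childbearing potential must have a negative serum or urine pregnancy test" shortly before treatment starts.
- **Tests on study (section 10, footnote 9).** This footnote is restricted to WOCBP: "A serum or urine pregnancy testing is required prior to study enrollment and prior to each cycle".

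No other FSH criterion appears in the protocol, and the study calendar lists no FSH test.

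**The concern.** The FSH sentence directly follows the definition of menopause and applies only to the younger women within it. Its evident purpose is laboratory confirmation where amenorrhea alone is less secure. If FSH rises at menopause, a confirming limit has to be a floor, and the text sets a ceiling. The words are written out in full, so this is not a symbol lost when the PDF was read, and it is current text.

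The safeguards exist because, in the words of section 3.3.9, "nivolumab and ipilimumab have the potential for teratogenic or abortifacient effects", and that section adds that the risk may extend to blinatumomab. A site that follows the criterion exactly would withdraw protection from the women in this group whose FSH gives least support to menopause, and impose testing and contraception on those whose FSH gives most.

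**Working it through.** No sample size, power or error rate is involved. The check is to apply the rule as written to each kind of woman. The FSH values 10 and 80 mIU/mL are illustrations either side of the limit of 40, not figures from the protocol.

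**Where the FSH limit decides.** Take a woman of 50 with 12 months of amenorrhea, no other identified cause and no surgical sterilization. She meets the clinical definition, and being under 55 she must also meet the FSH condition.

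- FSH 10: 10 < 40, so the condition is met. She is postmenopausal and exempt from contraception. On the evident reading of the WOCBP definition she is also exempt from pregnancy testing.
- FSH 80: 80 is not below 40, so the condition fails. She is not postmenopausal and stays WOCBP, with testing and contraception.

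**Where the FSH limit does not decide.**

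- Aged 45 or younger: fails the clinical definition and stays WOCBP at any FSH.
- Fewer than 12 months of amenorrhea: the same.
- Amenorrhea put down to another cause, including prior treatment: the same.
- Aged 55 or older: no FSH value is asked for.
- Surgically sterilized: exempt from contraception whatever her FSH.

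The inversion is therefore confined to women over 45 and under 55 (46 to 54 in completed years) with 12 months of otherwise unexplained amenorrhea and no surgical sterilization.

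**Which safeguards are lost.** The contraception exemption names postmenopausal women directly, so it follows however the WOCBP definition is parsed. Testing is less certain. The definition joins its two conditions with "or": past menarche AND (not sterilized OR not postmenopausal). Parsed strictly, an unsterilized postmenopausal woman is still WOCBP and would still be tested. The contraception sentence, however, treats menopause and sterilization as alternative routes out of childbearing potential, so the evident intent is that either one suffices. On that reading testing is lost too.

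**How many women.** The planned enrollment table in section 13.5 shows 9 + 3 = 12 women among 30 patients and gives no ages. The same section sets the maximum sample at 36, so 12 is not a ceiling. The documents give no basis for estimating how many women fall in the affected group.

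**The case against.** **The clinical definition already screens out the difficult cases.** A reader might infer that the error exposes any woman under 55 with a low FSH, and above all women whose periods stopped after chemotherapy or transplant. The documents do not support that. FSH is an added condition, and amenorrhea counts only when no other cause explains it. Section 3.2.1 admits newly diagnosed patients only from age 60, so every eligible woman aged 46 to 54 has had prior therapy. If her amenorrhea may be due to that therapy, she remains WOCBP before FSH is considered. This stands, and it narrows the gap considerably. It does not close it, because attributing a cause is a judgment.

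**The note is loosely drafted throughout.** The strict parse of the WOCBP definition would keep testing in place, so it goes too far to say that testing is certainly lost. This stands as a qualification on testing; the contraception exemption is unaffected.

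**The FSH sentence might mean something else.** It could be read as an entry condition for all women under 55, but that makes no sense in a note that defines WOCBP. It could be read as a test for being WOCBP, in which case the direction would fit. But the sentence adds to the menopause definition, and on that reading a menstruating woman with no FSH on file would fall outside WOCBP.

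**Other protections remain.** Pregnancy is an exclusion whatever the label, and a woman who suspects pregnancy must tell her physician. Investigators may also apply the usual direction from habit. None of these replaces a scheduled test, and the last means departing from the written criterion.

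**Conclusion.** The criterion is wrong as written. Two points of reading support this: FSH rises at menopause, which is general physiology assumed here, and the FSH sentence is there to confirm menopause, which its position and wording indicate. Given both, the limit sorts women in the affected group opposite to its purpose. Loss of the contraception requirement follows directly. Loss of pregnancy testing follows on the evident reading of the WOCBP definition.

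The group is probably small and cannot be counted. Nothing in the documents shows that any enrolled woman was misclassified. The error touches no endpoint, DLT rule, sample size or analysis. It deserves correction because it sits in a safety definition where exact compliance gives the wrong result, not because it is likely to be frequent.

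**What to change.** The sponsor should reconcile the direction of the FSH limit in 3.2.10 with the menopause definition it is meant to confirm. Women under 55 who do not meet the corrected criterion should remain WOCBP under the testing and contraception rules already in the protocol. The same amendment can clear up the "or" in the WOCBP definition, so that the testing requirement no longer depends on how it is parsed. Sites should check the recorded status of any enrolled woman aged 46 to 54 classed as postmenopausal.

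The cost is a short wording amendment and a small record check. Section 3.2.10 already requires a documented FSH, so the correction adds no new requirement in principle. Because the calendar in section 10 omits the test, it should be made consistent, and the record check may find values missing. Any woman reclassified as WOCBP takes on the existing testing and contraception requirements.
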